#### 10.1.2 Serious Adverse Events (SAEs)

Each AE must be classified by the investigator as SERIOUS or NONSERIOUS. An AE that meets 1 or more of the following criteria/outcomes is classified as serious:

- Death
- Life-threatening (see paragraph below on Life-threatening)
- In-patient hospitalization or prolongation of existing hospitalization (see paragraph below on Hospitalization)
- Persistent or significant disability/incapacity (see paragraph below on Disability)
- Congenital anomaly/birth defect
- Is considered a medically important event not meeting the above criteria, but which may jeopardize a subject, or may require medical or surgical intervention to prevent one of the criteria listed in this definition.

Serious also includes any other event that the investigator or sponsor judges to be serious. If there is any doubt whether the information constitutes an AE or SAE, the information is to be treated as an SAE.

**Life-threatening** – Any event in which the subject was at risk of death at the time of the event; 'life-threatening' does not refer to an event which hypothetically might have caused death if it were more severe.

**Hospitalization** – Hospitalization is defined as an overnight admission with observation of a minimum of 24 hours. A hospitalization planned before the start of the study for a pre-existing condition that has not worsened during the AE reporting period does not constitute an SAE.

**Disability** – Defined as a substantial disruption in a person's ability to conduct normal life functions.

## **10.2 Eliciting Adverse Event Information**

The investigator is to report all directly observed AEs and all AEs spontaneously reported by the study subject. In addition, each study subject will be questioned about AEs at each visit following the initiation of treatment.

## **10.3 Reporting**

Each AE is to be classified by the investigator as SERIOUS or NONSERIOUS.

All AEs that occur in study subjects during the AE reporting period specified in the protocol must be reported, whether or not the event is considered related to study medication.

### **10.3.1 Reporting Period**

The AE reporting period for a subject begins upon receiving the first dose of study medication and ends at the final protocol-required visit. In addition, SAEs that occur after the protocol-defined AE reporting period that are considered to be related to the study medication should be recorded and reported to the sponsor's medical monitor or CRO designee.

### **10.3.2 Reporting AEs**

NONSERIOUS AEs are to be reported on the AE CRFs.

### **10.3.3 Reporting SAEs**

Any SAE, regardless of causal relationship, must be reported to the sponsor's medical monitor/medical director or CRO designee **within 24 hours** after the investigator becomes aware of the SAE. Compliance with this time requirement is essential so that the sponsor may comply with its regulatory obligations.

The initial SAE report should be completed as fully as possible but should contain, at a minimum:

- Subject number/ID, sex, and age/date of birth
- The date of report
- Name of the reporter
- Description of the event, including event term(s), seriousness criteria, and a clinical summary of the event
- Causality assessment

Information about all SAEs (either initial or follow-up information) should be collected and recorded in English on the SAE Report Form. The investigator must assess the relationship to each specific component of the study treatment. If the event meets serious criteria, SAE Report Form should be sent to the CRO via email or fax, or the investigator should call the CRO SAE hotline within 24 hours of being made aware of the SAE (reference the site manual for contact information).

The investigator must report follow-up information relating to an SAE to the sponsor's medical monitor/medical director or CRO designee within 24 hours of awareness by submitting a new SAE Report Form. The subject should be observed and monitored carefully until the condition resolves or stabilizes.

All deaths are to be thoroughly investigated and reported. Autopsy reports are to be obtained, if possible, and sent to the CRO via email or fax.

The sponsor and/or its designee are responsible for reporting SAEs to all applicable regulatory agencies and the central ethics committees within the required timeline.

The investigators are responsible for submitting required safety information to their local Institutional Review Board (IRB) or Independent Ethics Committee (IEC) per local regulations. This information includes but is not limited to, any safety alert letter received from the sponsor and any SAEs occurring at their investigative site.

#### 10.3.4 Relationship to Study Medication

The causal relationship of the AE to study medication will be assessed by both the investigator and the sponsor.

The assessment of causal relationship to study drug should be evidence-based, and not based on the premise that all AEs are possibly causally related to study drug until proven otherwise.

Examples of evidence that would suggest a causal relationship between the drug and the AE include the occurrence of an AE that is uncommon and known to be strongly associated with drug exposure (eg, angioedema, hepatic injury, Stevens-Johnson Syndrome), or an AE that is uncommon in the population exposed to the drug.

The causal relationship of the AE is assessed using a binary system, and AEs are classified as either 'related' or 'unrelated':

**Related:** There is 'reasonable possibility' that the drug caused the AE. The AE follows a reasonable temporal sequence from the time of drug administration. There is supportive evidence (facts) to suggest a possible causal relationship, irrespective of the degree of certainty between the observed AE and the drug.

**Unrelated:** An AE does not follow a reasonable temporal sequence from administration of the product and/or there is no reasonable possibility that the drug caused the AE. This assessment includes situations where the AE is related to other factors such as the subject's clinical state, other therapeutic interventions, or concomitant drugs administered to the subject.

Default assessments using the 'related' category without supportive evidence for a causal relationship to study drug is generally uninformative and does not contribute meaningfully to the development of the safety profile of the drug or to subject protection.

Investigators are encouraged to choose the most plausible cause for the event(s) from the following list: medical history, lack of efficacy/worsening of treated condition, study treatment, other treatment (concomitant, or previous), withdrawal of study treatment, administration error, protocol-related procedure, others (specify).

#### 10.3.5 Severity

The investigator will assess each AE as either MILD, MODERATE, or SEVERE using the following guidelines to describe the maximum severity of the AE:

- **MILD:** Does not interfere with subject's usual function.
- **MODERATE:** Interferes to some extent with subject's usual function

- **SEVERE:** Interferes significantly with subject's usual function.

Note that a **severe** AE is not necessarily a **serious** AE. For example, a headache may be severe in intensity, but would not be classified as serious unless it met 1 of the criteria for serious events listed above.

#### 10.3.6 Follow-Up of Unresolved Events

All AEs should be followed until they are resolved or the investigator assesses them as chronic or stable or the subject's participation in the trial ends.

In addition, all SAEs and those non-serious events assessed by the investigator as related to the study medication should continue to be followed even after the subject's participation in the trial is over. Such events should be followed until they resolve or until the investigator assesses them as "chronic" or "stable." Resolution of such events is to be documented on the appropriate CRF.

#### 10.3.7 Special Situations

Certain safety events, called 'Special Situations', that occur in association with study medication(s) may require reporting. These Special Situations include, but are not limited to, the following:

- Overdose of the medicinal product
- Suspected abuse/misuse of the medicinal product
- Inadvertent or accidental exposure to the medicinal product
- Medication error involving the medicinal product (with or without subject/patient exposure to the sponsor's medicinal product, eg, name confusion)
- Drug-drug interaction

Special situations should be reported on the Special Situations CRF whether they result in an AE/SAE or not. Special situations with associated AE/SAE should also be reported on the corresponding AE/SAE forms, following applicable AE or SAE process.

### 10.4 Exposure In Utero

A pregnancy in a female subject must be confirmed by a positive serum  $\beta$  human chorionic gonadotropin ( $\beta$ -HCG) test.

The study medication should be immediately discontinued once the pregnancy of a female study participant has been confirmed.

If any study participant becomes or is found to be pregnant while receiving a study medication or within 30 days of discontinuing the study medication, the pregnancy must be recorded on the Pregnancy Reporting Form/Exposure In Utero Form within 24 hours of awareness of the pregnancy and sent to the CRO via email or fax, or the investigator should call the CRO SAE hotline within 24 hours of being made aware of the pregnancy (reference the site manual for contact information).

Pregnancy during this time frame of the female partner of a male subject should also be reported.

The investigator will follow the subject (or female partner of a male subject) until completion of the pregnancy. If the outcome of the pregnancy meets the criteria for immediate classification as

an SAE (ie, spontaneous abortion, stillbirth, neonatal death within 1 month of birth, or congenital anomaly [including that in an aborted fetus]), the investigator should follow the procedures for reporting an SAE within 24 hours of awareness. A pregnancy in and of itself is not considered an AE; however, unexpected complications are considered AEs.

Additional information about pregnancy outcomes follows:

- Note that “spontaneous abortion” includes miscarriage and missed abortion.
- All neonatal deaths that occur within 1 month of birth should be reported, without regard to causality, as SAEs. In addition, any infant death after 1 month that the investigator assesses as related or unrelated to the in utero exposure to the study medication should also be reported.
- In the case of a live birth, the “normality” of the newborn can be assessed at time of birth.
- The “normality” of an aborted fetus can be assessed by gross visual inspection unless there are pre-abortion laboratory findings suggestive of a congenital anomaly.

## 11 DATA ANALYSIS

### 11.1 Primary Endpoint and Sample Size Determination

The primary objective of this study is to quantify the dose-response relationship between oral vadadustat once daily dosing for 6 weeks and change in Hb in Japanese subjects with NDD-CKD in order to define the starting dose for use in Phase 3 clinical studies in Japan.

Change in Hb is defined as the Hb measured at the EOT visit minus the mean pre-treatment Hb. Pre-treatment Hb is defined as the average of 2 Hb values obtained prior to treatment based on the qualifying screening Hb value and the Hb value at the baseline visit. Linear regression analysis will be used to calculate the relationship between vadadustat dose and change in Hb.

The target enrollment will be approximately 48 subjects for the study with 12 subjects enrolled in each of the 4 treatment groups.

Based on the results from Study AKB-6548-CI-0005 that was conducted in the United States and evaluated vadadustat in patients with anemia secondary to NDD CKD, it is reasonable to assume that the expected mean Hb changes from baseline to Week 6 will be 0, 0.5, 0.7, and 1.2 g/dL for the placebo, 150 mg, 300 mg, and 600 mg vadadustat dose groups, respectively, with a common standard deviation of 0.68 g/dL among the 4 treatment groups. With these assumptions, the study will have >85% power to detect a non-zero slope in a dose-response relationship using linear regression analysis and  $\alpha=0.05$ , based on simulation of 10,000 repetitions using SAS® software, Version Number 9.4.

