### 5.1 Primary Objective and Endpoint

The primary objective of this study is to assess the dose-response relationship between oral vadadustat once daily dosing for 6 weeks and the change in Hb in Japanese subjects with anemia secondary to NDD-CKD; in order to define the starting dose for use in Phase 3 clinical studies in Japan.

The primary endpoint that will be used to assess this objective is the mean change in Hb levels from pre-treatment to the end of the primary efficacy period (Week 6).

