### 9.3.7 Week 10 Visit (End-of-treatment visit for the blinded period and early withdrawals)

All enrolled subjects who receive at least 1 dose of blinded study drug should complete the Week 10 assessments.

Subjects who withdraw early from the study prior to the Week 6 visit or permanently discontinue study medication prior to the Week 6 visit, should undergo the clinical and laboratory assessments specified below within 1 day of stopping study medication, if possible. Such subjects should also complete the requisite 2-week safety follow-up period (see [Section 9.3.10](#)).

Individual subject data (up to Week 6) will be locked after the Week 6. Following data lock, individual subject's randomized treatment assignment will be unblinded and the subject will be informed at the Week 10 visit. Subjects who were assigned to receive placebo will discontinue from the study at the end of the Week 10 visit, and subjects who were assigned to receive vadadustat will continue to the open-label extension period.

At the Week 10 visit, the following activities/procedures will be performed:

- Vital signs (heart rate and blood pressure should be assessed in a seated position after 5 minutes of rest and prior to blood draws)
- AE review (see [Section 10.3.6](#) for follow-up of unresolved events)
- Concomitant medication review
- Laboratory procedures:
  - Hb using HemoCue for dose adjustment (not for subjects who discontinue prior to the Week 6 visit)
  - CBC
  - Serum chemistry and eGFR

- Iron indices
- Hepcidin
- C-reactive protein
- VEGF
- Dispense open-label vadadustat (as necessary; only applicable to subjects who are continuing to the open-label extension period)
- Subjects should be questioned regarding dosing compliance
- Review dosing instructions (only applicable to subjects who are continuing to the open-label extension period)

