### 11.5 Efficacy and PD Analyses

The entire set of efficacy outcomes will be defined in the statistical analysis plan (SAP). In addition to the primary endpoint analysis defined above, the following efficacy endpoints will also be assessed:

- Actual values and change (absolute and percent) from baseline in Hb, HCT, RBC count, and reticulocyte count (both absolute and percent)
- Actual values and change (absolute and percent) from baseline in iron, TIBC, TSAT, ferritin (both absolute and percent), and hepcidin

For purposes of analysis, a pre-treatment average (defined as the average of 2 samples obtained prior to treatment [ie, the qualifying screening value and baseline value]) will be used as the baseline value for Hb and RBC count, and last observation before the first dose of study medication will be used as baseline for other parameters.

Changes from baseline of efficacy and PD parameters will be summarized using descriptive statistics by treatment groups and each scheduled assessment, and results will be displayed using box plots.

Linear regression analysis will be performed for Hb change from baseline to Week 6, to assess the vadadustat dose-response relationship. Similar analysis will be performed for change from baseline to Week 6 of reticulocyte count (both absolute and percent), hematocrit, and RBC count.

Also, similar linear regression analysis will be performed for change from baseline to Week 6 of the iron indices (ie, iron, TIBC, ferritin, and TSAT) and hepcidin will be evaluated.

All tests of significance will be performed using a 0.05 two-sided significance level.

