## Appendix A: Schedule of Activities

Please refer to [Section 9.2](#) for detailed information regarding the study procedures and evaluations, and please refer to [Section 9.3](#) for detailed information regarding the activities to be performed at each study visit.

	Screening	Primary efficacy period (blinded, fixed-dose treatment) (Day 1-Week 6)					Blinded dose adjustment, data cleaning period (Week 7-10)	Open-label extension period (Week 11-16)		Safety Follow-up (Week 17-18)
Study Week	-4 to 0	Base line	1	2	4	6	10 (EOT, Blinded Period)	14	16 (EOT, Open-Label Period)	18
Study Day	-28 to -4	1	8	15	29	43	71	99	113	127
Visit Window (Days)			±1	±1	±3	±3	±3	±3	±3	±3
Informed consent	X									
Review inclusion/exclusion criteria	X	X								
Individual subject data lock (for subjects who complete Week 6)							X			
Individual subject unblinding (for subjects who complete Week 6)							X			
Demographics, medical history, physical exam, and weight	X									
Vital signs	X	X	X	X	X	X	X	X	X	X
12-lead electrocardiogram		X								
Adverse event review			X	X	X	X	X	X	X	X
Concomitant medication review	X	X	X	X	X	X	X	X	X	X
Serum pregnancy test	X								X	
Urine pregnancy test		X								
Coagulation tests		X								

	Screening	Primary efficacy period (blinded, fixed-dose treatment) (Day 1-Week 6)					Blinded dose adjustment, data cleaning period (Week 7-10)	Open-label extension period (Week 11-16)		Safety Follow-up (Week 17-18)
Study Week	-4 to 0	Base line	1	2	4	6	10 (EOT, Blinded Period)	14	16 (EOT, Open-Label Period)	18
Study Day	-28 to -4	1	8	15	29	43	71	99	113	127
Visit Window (Days)			±1	±1	±3	±3	±3	±3	±3	±3
Folate and vitamin B12	X									
Hb using HemoCue® (Week 10 assessment is not for subjects who discontinue prior to Week 6)			X	X	X	X	X	X		
Complete blood count, including Hb [a]	X	X	X	X	X	X	X	X	X	X
Serum chemistry and eGFR	X	X		X	X	X	X	X	X	X
Iron indices	X	X		X	X	X	X		X	
Hepcidin		X				X	X			X
C-reactive protein		X				X	X			X
VEGF		X				X	X			X
PK pre-dose sample (study drug to be administered after sample collection)					X					
Blinded study drug dispensation, as necessary		X		X	X	X				
Blinded study drug dosing		Blinded study drug dosing								
Vadadustat dispensation, as necessary [b]							X	X		
Vadadustat dosing [b]								Open-label vadadustat dosing		
Study drug compliance check			X	X	X	X	X	X	X	

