### 5.1 Primary Objective and Endpoint

The primary objective of this study is to assess the dose-response relationship between oral vadadustat once daily dosing for 6 weeks and the change in Hb in Japanese subjects with anemia secondary to NDD-CKD; in order to define the starting dose for use in Phase 3 clinical studies in Japan.

The primary endpoint that will be used to assess this objective is the mean change in Hb levels from pre-treatment to the end of the primary efficacy period (Week 6).

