### 7.6.3 Individual Subject Discontinuation during the Primary Efficacy Period or Blinded Dose Adjustment and Data Cleaning Period

Subjects discontinuing study medication or withdrawing early from the study during the blinded periods should undergo the Week 10 (EOT for blinded period) clinical and laboratory assessments within 1 day of stopping study medication, if possible. Such subjects should also complete the 2-week safety follow-up period (see Appendix A). For subjects who discontinue

study medication, the investigator should resume standard of care treatment, as deemed appropriate.

If a subject does not return for a scheduled visit, every effort should be made to contact the subject.

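### Section 11.1 takes the primary Hb value from the EOT visit, a label the protocol gives to Weeks 10 and 16 or to early stopping, while the rest of the protocol specifies Week 6

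*Protocol*

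**What the plan says.** Section 11.1, headed as the primary endpoint section, states: "Change in Hb is defined as the Hb measured at the EOT visit minus the mean pre-treatment Hb". The sentence is the same in both protocol versions in the file that show Section 11.

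The EOT label is used as follows:
- Appendix A heads two visit columns with it: "10 (EOT, Blinded Period" and "16 (EOT, Open-Label Period". The Week 6 column does not carry it.
- Section 9.3.7 is titled "Week 10 Visit (End-of-treatment visit for the blinded period and early withdrawals". Section 9.3.9 gives Week 16 the same role for the open-label period, and Section 9.3.10 repeats both. Section 9.3.6, on the Week 6 visit, does not use the term.
- Section 7.6.3, on stopping before unblinding, says that such subjects "should undergo the Week 10 (EOT for blinded period) clinical and laboratory assessments within 1 day of stopping study medication", where this can be done.

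The time point of the primary endpoint is given elsewhere as Week 6. Section 5.1 calls it the "mean change in Hb levels from pre-treatment to the end of the primary efficacy period (Week 6"), and the synopsis agrees. Section 11.5 states: "Linear regression analysis will be performed for Hb change from baseline to Week 6, to assess the vadadustat dose-response relationship". The planning means in Section 11.1 are also changes from baseline to Week 6.

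**The concern.** The primary objective is the relation between dose and Hb change over 6 weeks of once-daily dosing, used to define a Phase 3 starting dose. For that, Hb must be measured while subjects are still on their randomised dose, apart from the safety reductions and stops of Section 8.2.4. From the Week 6 visit onwards the dose is adjusted towards an Hb of 10-12 g/dL, so Hb at Week 10 or Week 16 partly reflects doses chosen in response to earlier Hb. Regressing it on randomised dose estimates something else.

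Two further features make the label matter:
- Only data from screening to Week 6 are cleaned and locked before each subject is unblinded. Week 10 Hb lies outside that lock, and placebo subjects leave at Week 10, so Week 16 has no placebo arm.
- For subjects who stop early, the EOT rule takes the value at stopping, whenever that was.

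With 12 subjects per group, and unblinding that proceeds subject by subject, the visit that supplies the primary value should be stated once and in the same way everywhere.

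**Working it through.** **1. What each wording takes, by type of subject** (Sections 7.6.3, 8.2.4, 8.2.7, 9.3.6 to 9.3.9, and Appendix A of the second version)
- Placebo completer: the EOT wording gives Week 10 (Day 71); the Week 6 wording gives Day 43.
- Vadadustat completer: the EOT wording gives Week 10 (Day 71) or Week 16 (Day 113), and the sentence does not say which. The Week 6 wording gives Day 43.
- Subject who stops before Week 6: the EOT wording gives a value within 1 day of stopping, so before Week 6. The Week 6 wording gives no scheduled value.

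Stopping is required in Weeks 1 to 6 after an excess Hb response at 1 tablet, or after a second excess response following a reduction (Section 8.2.4). It therefore depends on both response and tablet count. The MITT population needs only one post-baseline value (Section 11.2.2), so such subjects belong to it. Whether their stopping value enters the regression depends on which wording is followed.

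**2. The plan's own power figure**

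Inputs from Section 11.1: doses 0, 150, 300 and 600 mg; mean changes 0, 0.5, 0.7 and 1.2 g/dL; SD 0.68; 12 per group; two-sided alpha 0.05.
- Mean dose 262.5; deviations −262.5, −112.5, 37.5 and 337.5; sum of squares 196,875 per subject set, × 12 = 2,362,500.
- Slope = (−112.5 × 0.5 + 37.5 × 0.7 + 337.5 × 1.2) / 196,875 = 375 / 196,875 = 0.00190 g/dL per mg, or 0.190 per 100 mg.
- Noncentrality = 0.0019048 × √2,362,500 / 0.68 = 4.31 on 46 df.
- Power: 98.7 to 98.8% from the noncentral t, 98.6% in 10,000 simulations.

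The claim of more than 85% is met. It already rests on Week 6 means, so correcting the definition changes no planning figure.

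**3. How far titration could reach by Week 10**

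Section 8.2.7 calls for one more tablet if Hb has risen by no more than 0.5 g/dL after the first 6 weeks. On the planning values, P(change ≤ 0.5) = Φ((0.5 − mean)/0.68):
- placebo Φ(0.735) = 0.769
- 150 mg Φ(0) = 0.500, or 6 of 12
- 300 mg Φ(−0.294) = 0.384, or 4.6 of 12
- 600 mg Φ(−1.029) = 0.152

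Only the 150 mg and 300 mg figures bear on exposure. An extra placebo tablet adds no drug, and the 600 mg arm is already at the 4-tablet maximum. These are shares meeting a trigger and do not measure bias.

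**4. Illustration of the possible effect**

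The protocol gives no Week 10 or Week 16 means. Assume that the active means move towards their average, (0.5 + 0.7 + 1.2)/3 = 0.8 g/dL, with placebo at 0 and SD 0.68:
- no convergence: slope 0.190 per 100 mg, power 98.6%
- half: slope 0.149, power 89.4%
- three quarters: slope 0.128, power 78.1%
- full: slope 0.107, power 61.4%

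Across the active doses alone, the slope falls from 0.157 per 100 mg to 0. That is the part of the curve that would separate one starting dose from another.

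**The case against.** The best reply is that no careful reader would be misled. Section 11.1 itself speaks of 6 weeks of dosing and plans on Week 6 changes. The synopsis, Section 5.1 and Section 11.5 name Week 6. The per-protocol population requires efficacy data through Week 6, and Hb change to Week 16 is a separate secondary endpoint. Section 11.5 also gives the Hb baseline, the time point and the method, so Section 11.1 is not the only definition of the variable. Because Week 6 is prespecified in several places and those data are locked before each unblinding, the room for choosing a visit afterwards is small.

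Most of this stands. A reader might infer that the primary analysis will be run on Hb after titration; the documents do not support that, since it would follow only if one sentence were put above all the others. A reader might also take the trigger shares as the size of the bias. They are not: dose decisions use HemoCue, which is not scheduled at baseline, while 0.68 is the planning SD of the endpoint, and investigators may depart from the guidelines.

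What does not fall away is the conflict itself. The sentence sits in the primary endpoint section, and Section 11.5 refers back to the primary endpoint analysis defined above it. Handling of a missing Week 6 value can ordinarily be left to the SAP, but here the protocol already states a rule for early stoppers, and that rule differs from its endpoint.

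**Conclusion.** The point holds as an internal contradiction in how the primary variable is defined. Section 11.1 names a visit that is never Week 6 in the protocol's own usage; the synopsis, Section 5.1, Section 11.5 and the planning assumptions name Week 6. Week 6 is clearly intended. Followed literally, the Section 11.1 rule would change the quantity estimated: values after dose adjustment for completers, and values at stopping for those who leave early.

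The planned power is unaffected (about 98.6% against a stated more than 85%). The size of the distortion under the literal rule cannot be derived, because no Week 10 or Week 16 means are given. The range from 98.6% down to 61.4% power rests wholly on the assumed convergence, with placebo at 0 and SD 0.68.

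One limit applies: the last protocol version in the file breaks off in Section 8, so it cannot be seen whether the sentence survives there. Its synopsis and Section 5.1 still say Week 6.

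**What to change.** In Section 11.1, replace the reference to the EOT visit, for example: *Change in Hb is the central-laboratory Hb at the Week 6 visit (Day 43 ± 3 days) minus the mean pre-treatment Hb.* Naming the central laboratory is a useful clarification, because Hb is also measured by HemoCue for dosing decisions.

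Add one sentence stating whether an Hb taken at early termination before Week 6 enters the primary regression; changing the visit name alone leaves that open.

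Check Section 11.1 of the latest protocol version and the SAP, and use the same wording in both. Superseded versions need no edit.

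The cost is two sentences. No change to sample size, schedule or data collection follows.
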